6.1.2 Routine practice group

In the control group, PsA risk will be assessed in moderate to severe PsO patients as per routine practice without using the EARP screening. Routine practice for the treatment of moderate to severe PsO patients seldom include active screening for symptoms of PsA using any screening questionnaires. Instead of that, the investigator may ask the participants if they have any joint pain currently or in the past. After the completion of PsA risk assessment via routine practice according to the investigator's judgement, the participants will be evaluated using the CASPAR.

6.2 Participant numbering, randomization

6.2.1 Participant numbering

Each participant is identified in the study by a participant number (Participant No.), that is assigned when the participant is enrolled for screening and is retained for the participant throughout his/her participation in the study. The Participant No. consists of the site number (as assigned by Novartis to the investigative site) with a sequence number suffixed to it, so that each participant's participation is numbered uniquely across the entire database.

6.2.2 Randomization

The randomization numbers will be generated using the following procedure to ensure that treatment assignment is unbiased.

Participants who meet all inclusion criteria and none of the exclusion criteria will be centrally, randomly allocated with a 1:1 ratio to either the EARP group or the Routine practice group using an Interactive Web Response System (IWRS).

The Randomization Number (Randomization No.) consists of the group number and a sequence number. An eligible patient will be given the lowest available sequence number. This number assigns the patient to one of the groups.

Randomization will be stratified by the site in order to minimize the bias caused by each judgment of investigator.

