4.1 Rationale for study design

This is a randomized, open, parallel, controlled, multi-center, interventional, cross-sectional study to evaluate the detection rate of PsA in Korean moderate-to-severe PsO patients, with or without active screening for arthritis in PsO.

The EARP questionnaire, an intervention in this study, is used for early diagnosis of PsA. In order to evaluate the usefulness of early diagnosis of PsA through the EARP questionnaire, the control group is designed to screen subjects suspected of have PsA according to the routine practice of real-world dermatology setting. According to the characteristics of the intervention used for early diagnosis of PsA in each group, this study is designed as an open study. Therefore,

1:1 balanced randomization is planned to compensate for the limitation of the open study and to reduce the bias.

Regarding the study population, this study will include male and female patients with moderate to severe PsO. It is confirmed that the PASI score, which evaluates the severity of PsO, was significantly higher in PsO patients with PsA than in PsO patients without PsA. This means that there is a close relation between the severity of PsO and the prevalence of PsA (Choi JW, et al. 2017). Therefore, in order to conduct the study on patients expected to have a high prevalence of PsA, patients with a PASI score of 10 or higher, defined as moderate to severe PsO patients, are selected as a study population. In addition, this study excluded patients who has ever received the biologic Disease-Modifying Anti-Rheumatic Drugs (DMARDs) which may mask symptoms of PsA and thus make PsA more difficult to be diagnosed in PsO patients. By excluding these patients, the effect of the questionnaire can be confirmed more clearly in the real-world setting.

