4.6 Rationale for Public Health Emergency mitigation procedures

Not applicable

5 Study Population

The study will include male and female patients with moderate to severe PsO. A total of 368 patients (184 in each treatment arm) will be randomized at 15 centers across the Korea (Depending on the progress of the study, additional sites may be added.).

The calculation of the sample size is provided in Section 12.8.

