11.3 Site monitoring

Before study initiation, at a site initiation visit or at an investigator's meeting, a Novartis/CRO representative will review the protocol and data capture requirements (i.e. eCRFs) with the investigators and their staff. During the study, Novartis employs several methods of ensuring protocol and GCP compliance and the quality/integrity of the sites' data. The field monitor will visit the site to check the completeness of participant records, the accuracy of data capture / data entry, the adherence to the protocol and to GCP, the progress of enrollment, and to ensure

that study treatment is being stored, dispensed, and accounted for according to specifications. Key study personnel must be available to assist the field monitor during these visits.

The investigator must maintain source documents for each participant in the study, consisting of case and visit notes (hospital or clinic medical records) containing demographic and medical information, laboratory data, and the results of any other tests or assessments. All information on CRFs must be traceable to these source documents in the participant's file. The investigator must also keep the original ICF signed by the participant (a signed copy is given to the participant).

The investigator must give the monitor access to all relevant source documents to confirm their consistency with the data capture and/or data entry. Novartis monitoring standards require full verification for the presence of informed consent, adherence to the inclusion/exclusion criteria and of data that will be used for all primary variables. Additional checks of the consistency of the source data with the CRFs are performed according to the study-specific monitoring plan. No information in source documents about the identity of the participants will be disclosed.

12 Data analysis and statistical methods

All analyses will be performed by a designated CRO.

Descriptive statistics will include n, mean, standard deviation, median, minimum, and maximum for continuous variables and the number and percentage of patients for categorical variables. If necessary, more detailed information will be provided. Statistical comparisons between two groups for continuous variables will be made using independent t-test or Wilcoxon rank sum test, and that for categorical variables using Chi-square test or Fisher's exact test. All the statistical tests will use a two-sided test at the significance level of 0.05.

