Missing data will not be imputed, and all statistical analyses will be performed using available data.

Further technical details will be specified in the Statistical Analysis Plan, which will be finalized prior to database lock.

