12.4.2 Statistical model, hypothesis, and method of analysis

The following hypothesis will be tested at a two-sided 0.05 level.

$$H_0: P_I = P_C \text{ vs. } H_a: P_I \neq P_C$$

where P_I and P_C are the percentage of patients with PsA in each EARP group and Routine practice group, respectively.

The number and percentage of patients with PsA will be presented by each group using the FAS. The point-estimate for the difference of proportion between two groups (EARP group – Routine

practice group) will be given with its two-sided 95% Confidence Interval (CI) and the p-value for the null hypothesis. Superiority will be claimed if the lower limit of the CI is greater than 0.

The primary analysis will be repeated for the PPS using the same model as the one used for the primary analysis.

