2.1 Data analysis general information

All analyses will be performed by a designated Contract Research Organization (CRO) using the SAS software (Version 9.4).

Descriptive statistics will include the number of participants, mean, standard deviation, median, minimum, and maximum for continuous variables, and the number and percentage of participants for categorical variables. If necessary, more detailed information will be provided. For continuous data, statistical significance for differences between the two groups will be tested by Independent t-test if normality is met, or Wilcoxon rank sum test if normality is not met. For categorical data, statistical significance for differences between the two groups will be tested by Chi-square test. If cells with an expected frequency of <5 exceed 20% of all cells when testing for differences between the groups, Fisher's exact test will used instead of Chi-square test.

All the statistical tests will use a two-sided test at the significance level of 0.05. Statistical summaries will be presented to two decimal places, and p-values to three decimal places.

Prior/concomitant PsO related treatments and other medical history will be coded using the MedDRA (latest version at time of analysis) System Organ Class and Preferred Term and listed in descending order by incidence for the study groups. Prior/concomitant medications will be coded using the WHO Drug Dictionary (latest version at time of analysis) Therapeutic Main Group and Preferred Name and listed in descending order by incidence for the study groups.

Missing data will not be imputed, and all statistical analyses will be performed using available data.

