2.4.2 Statistical hypothesis, model, and method of analysis

To compare PsA detection rates between the EARP group and the Routine practice group, the following hypothesis will be tested at a two-sided 0.05 level.

$$H_0: P_I = P_C vs. H_a: P_I \neq P_C$$

where P_I and P_C are the detection rate of PsA in the EARP group and the Routine practice group, respectively.

English SAP Version 01 (release date: 15Jun2023)

The number of participants with true positive and the detection rate of PsA will be presented by each group using the FAS. The point-estimate of the difference in detection rate between the two groups (EARP group - Routine practice group) will be given with its two-sided 95% Confidence Interval (CI) and the p-value for the null hypothesis. If the lower limit of the twosided 95% CI of the difference between the two groups is greater than 0, the EARP group is deemed superior to the Routine practice group.

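### Randomisation is stratified by site but the primary comparison ignores site; a site-stratified risk difference would be a cheap, low-priority improvement

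*Protocol*

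**What the plan says.** Protocol 6.2.2 allocates 1:1 through a central web system and adds: "Randomization will be stratified by the site in order to minimize the bias caused by each judgment of investigator". Protocol section 5 says that patients "will be randomized at 15 centers across the Korea" and that sites may be added. On balance, Protocol 4.1 says only that "1:1 balanced randomization is planned to compensate for the limitation of the open study and to reduce the bias". Neither document mentions blocks.

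For the primary endpoint, SAP 2.4.2 says that the difference in detection rate (EARP minus routine practice) "will be given with its two-sided 95% Confidence Interval (CI) and the p-value for the null hypothesis". Protocol 12.4.2 sets the decision rule: "Superiority will be claimed if the lower limit of the CI is greater than 0". SAP 2.4.2 gives the same rule. Neither section names an interval method, a model or a site term.

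Protocol section 12 leaves room for this: "Further technical details will be specified in the Statistical Analysis Plan". The SAP does not use that room for the primary analysis. What remains is the general rule in SAP 2.1, that for categorical data "statistical significance for differences between the two groups will be tested by Chi-square test", with Fisher's exact test when expected counts are small. Protocol section 12 has a matching line: "that for categorical variables using Chi-square test or Fisher's exact test". Both are unstratified. Protocol 12.4.3 plans no sensitivity analysis, and SAP 2.4.3 only repeats the analysis on the per-protocol set. No planned analysis uses site.

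**The concern.** When allocation is stratified, the usual practice is to analyse by the same factor. If sites differ in detection rate and the arms are balanced within sites, the differences between sites largely cancel out of the arm comparison. The crude variance still counts them, so the interval is a little too wide and the test rejects a little too seldom. Power that the randomisation has already paid for is then left unused.

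Shared site effects are plausible here. A true positive requires CASPAR ≥ 3 in both arms (Protocol 12.4.1), and CASPAR is assessed in every participant (Protocol 8.5.1.1). Case mix or joint assessment at a site would therefore move both arms together. The planned evaluable number gives barely 80% power, so a small gain has some value.

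**Working it through.** **Inputs.** Two-sided alpha 0.05, power 0.80, rates of 9% (routine) and 19.7% (EARP), and 10% invalid cases (Protocol 12.7, SAP section 3); 15 sites (Protocol section 5). The between-site SD is not in the documents, so it is assumed and shown as a range. Blocks of 4 are also assumed.

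**The plan's own figure.** n = (1.96 + 0.842)² × (0.09 × 0.91 + 0.197 × 0.803) / 0.107² = 164.64, so 165 per arm. 165 / 0.9 = 183.3, so 184 per arm and 368 in total. This reproduces. The same formula gives power of 80.1% at 165 and 84.2% at 184 per arm. The full analysis set requires a primary-endpoint assessment (Protocol 12.1), so 165 per arm is the relevant number for planned power.

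**Which test the general rule selects.** At the average rate of (9% + 19.7%) / 2 = 14.35%, the expected count of true positives is 0.1435 × 165 = 23.7 per arm. That is well above 5, so chi-square applies rather than Fisher.

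**Sparseness.** With equal sites there are 165 / 15 = 11 patients per arm per site and 0.09 × 165 / 15 = 1.0 expected routine-arm true positive per site. This favours a variance that holds with sparse strata over a fixed effect for each site.

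**Stratified estimator.** For site k, let x and y be the true positives among n₁ (EARP) and n₀ (routine), with n = n₁ + n₀.
- Difference: d = Σ[(x·n₀ − y·n₁)/n] / Σ[n₁n₀/n]
- Sato variance: (d·ΣP + ΣQ) / (Σ[n₁n₀/n])², where P = [n₁²y − n₀²x + n₁n₀(n₀ − n₁)/2]/n² and Q = [x(n₀ − y) + y(n₁ − x)]/(2n)
- Test: z = d / Sato SE; 95% CI: d ± 1.96 × Sato SE

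**Simulation.** Patients are spread over 15 sites with equal expected shares. A normal site effect on the logit scale is shared by both arms. Intercepts are set so that the overall rates stay at 19.7% versus 9% for power, or 14.35% in both arms for type I error.

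Power at 330 patients, blocks of 4:

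| Site SD (assumed) | Chi-square | Stratified |
|---|---|---|
| 0 | 80.7% | 80.9% |
| 0.5 | 80.4% | 81.4% |
| 1.0 | 81.1% | 83.9% |

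These are approximate. Exact enumeration with no site effect gives 80.3% for chi-square at 165 per arm, so differences of a few tenths of a point should not be read as real.

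Two-sided type I error at 368 patients, blocks of 4: chi-square 5.1% (SD 0), 4.7% (SD 0.5) and 3.9% (SD 1.0); stratified 5.1% to 5.2% throughout.

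**When the conditions fail.** Without blocking and with no site effect, power at 330 patients is about 80.1% for chi-square and 78.8% stratified, a loss of 80.1 − 78.8 = 1.3 points. Without blocking, the crude test is also not conservative: its type I error is 4.9% to 5.2% at 368 patients. If only routine judgement varies by site (SD 0.8, 368 patients), power is 81.6% versus 81.7% blocked and 81.6% versus 80.8% unblocked.

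**How large might the SD be?** The only spread in the documents is the four Korean prevalences in Protocol 12.7 (9.0%, 10.8%, 13.5%, 14.1%), whose logits have an SD of 0.235. These are differences between studies, not between sites, so the anchor is weak. At SD 0.24, 368 patients and blocks of 4, power is 84.6% versus 84.8%, a negligible gain.

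**The case against.** The strongest reply is that the stated reason for stratifying is variation in investigator judgement, and judgement acts as the screen only in the routine arm. In that scenario stratifying gains nothing, and it loses a little without blocking. Blocking is not stated, and gains above about 1 point need site SDs that no passage supports. The crude test is valid, so one sentence naming an unstratified interval would complete the plan. Most of this stands, and it is why the point is low priority. It does not remove the point: CASPAR enters the endpoint in both arms, so shared site variation is plausible, and blocking can be checked before the method is fixed.

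A reader might also infer that the unnamed interval is a serious error in its own right, because power at 184 per arm is 84.8% with a plain Wald interval and 80.5% with a continuity-corrected one. The documents do not support that. They mention no continuity correction, and the sample-size formula uses the uncorrected unpooled variance. A Wald interval and the chi-square test disagree on superiority in only 0.13% of trials at 184 per arm and 0.31% at 165. Both documents also give a single decision rule, the lower limit, so the p-value makes no competing claim.

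**Conclusion.** The point holds as an efficiency improvement of low priority. The trial randomises within site and no planned analysis uses site. With effects shared by both arms and blocked allocation, the crude test is mildly conservative, and stratifying adds from nothing to about 3 points of power over SDs of 0 to 1.0. With no blocking and little site variation it costs about 1.3 points and takes power just below 80%.

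It would be wrong to infer that leaving site out inflates type I error, invalidates the result or undermines the sample size. Crude type I error stays at or below about 5% in every scenario, and 164.64 reproduces. Nor would a site term remove bias from open assessment.

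Confidence is high that site is absent from the analysis. It is low on the size of any benefit, which rests on an assumed SD, assumed blocks of 4 and a shared site effect.

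**What to change.** First confirm from the randomisation system's specification that allocation is blocked within site, and record this in the SAP. Then, in SAP 2.4.2:
- Make the primary analysis the site-stratified Mantel-Haenszel risk difference with a Sato-variance 95% CI, keeping the rule that the lower limit must exceed 0.
- Take the two-sided p-value from the same estimate and standard error, so that interval and p-value give one decision. Pairing the Sato interval with a Cochran-Mantel-Haenszel p-value would give conflicting decisions in about 0.4% of blocked trials.
- Pre-specify how small sites, and sites with patients in only one arm, are pooled. With unequal sites, about 0.6 sites per simulated trial had no patients in at least one arm.
- Report the crude difference with a named interval, such as Miettinen-Nurminen, as supportive.

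Naming the interval method comes as a by-product. If allocation proves not to be blocked, weigh the loss of about 1.3 points before making the stratified method primary.

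The cost is a few lines of SAP text and a standard analysis. Site is already part of the participant number (Protocol 6.2.1), and sample size and conduct are unchanged.

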6.3 Blinding

Assigned group will be open to participants, investigator staff, persons performing the assessments and the Novartis clinical trial team (CTT). Such that no aggregate statistical analyses by treatment shall be performed prior to the database lock.

7 Informed consent procedures

Eligible participants may only be included in the study after providing (witnessed, where required by law or regulation), Institutional Review Board (IRB)-approved informed consent.

In cases where the participant's representative(s) gives consent, the participant must be informed about the study to the extent possible given his/her level of understanding. If the participant is capable of doing so, he/she must indicate agreement by personally signing and dating the written informed consent document.

Informed consent must be obtained before conducting any study-specific procedures (e.g. all of the procedures described in the protocol). The process of obtaining informed consent must be documented in the participant source documents.

Novartis will review the Contract Research Organization (CRO) proposed ICF to ensure it complies with the International Council for Harmonization of Technical Requirements for Pharmaceuticals for Human Use (ICH) E6 Good Clinical Practice (GCP) guidelines and regulatory requirements and is considered appropriate for this study. Any further changes to the proposed consent form suggested by the investigator must be agreed to by Novartis before submission to the IRB.

8 Visit schedule and assessments

The assessment schedule (Table 8–1) lists all of the assessments when they are performed. All data obtained from these assessments must be supported in the participant's source documentation.

All baseline assessments may occur during the screening, and all procedures for each participant is performed for one day (Visit 1). If an additional time is required depending on the circumstances of the institution and so on, the data specified in this study protocol are recommended to be collected as soon as possible.

Participants should be seen for all assessments as outlined in the assessment schedule (Table 8–1).

Table 8–1 Assessment schedule

Period	Screening	Randomization	Intervention	Physical examination	Evaluation
Visit Name	Visit 1				
Day/Week/Month	Day 1				
Obtain informed consent ¹⁾	X				
Demographics	Year of birth, age	X			
	Sex	X			
	Height (cm)	X			
	Weight (kg)	X			
	Body Mass Index (BMI)	X			
	Alcohol consumption status	X			
	Smoking status	X			
Pregnancy tests ²⁾	X				
Inclusion/exclusion criteria	X				
Medical history and medication ³⁾	Medical history	X			
	PsO related medical history	X			
	Medications	X			
	PsO related treatment other than medications	X			
Randomization			X		
Intervention	EARP screening (EAPR group)			X	
	Investigator's judgement (Routine practice group)			X	
Physical examination	NAPSI				X
	SJC66				X
	TJC68				X

Period	Screening	Randomization	Intervention	Physical examination	Evaluation
Visit Name	Visit 1				
Day/Week/Month	Day 1				
CASPAR ⁴⁾	Clinical assessment				X
	Blood test				X
	Radiography				X

PsO; Psoriasis; EARp: Early arthritis for psoriatic patients; NAPSI: Nail psoriasis severity index; SJC: Swollen joint count; TJC: Tender joint count; CASPAR: Classification criteria for psoriatic arthritis; PsA: Psoriatic arthritis

- 1) All procedures must be conducted after getting ICF, and participant numbers are assigned in the order of consent.
- 2) For all female patients of child bearing potential only, a urine-HCG test will be performed.

3) Medical history and medication

- Medical history: Heart diseases, stroke, diabetes, hyperlipidemia, hypertension, fatty liver and other diseases
- PsO related medical history: Date of diagnosis for PsO, family history of PsO, family history of PsA, PASI score, hard-to-treat area involvement (scalp, palmoplantar and nails), musculoskeletal symptoms
- Medications
- PsO related treatment other than medications

4) CASPAR: Based on the CASPAR, participants are diagnosed with or without PsA.

- Clinical assessment: Inflammatory articular disease (inflammatory joint (peripheral) disease, enthesitis, and inflammatory axial disease), date of diagnosis for PsO#, family history of PsO#, presence or absence of typical psoriatic nail dystrophy (onycholysis, pitting, hyperkeratosis), presence or absence of dactylitis, history of dactylitis (recorded by rheumatologist)
- Blood test: Rheumatoid factor
- Radiography: Hand and foot plain X-ray (evidence of juxta-articular new bone formation in hand (including wrist) and feet (including ankle))

Note) #: These values which are included the CASPAR are replaced by the values in Section 8.2.2.2.

